6.7.2.1. PNEUMONITIS

Pneumonitis has been reported in patients receiving Durvalumab.

Presentations of pneumonitis can range from asymptomatic lung infiltrates to those that mimic severe bacterial pneumonia. Early consideration of pneumonitis should be realised when patients present with new onset or worsening of respiratory symptoms such as dyspnoea or cough. Prompt treatment with steroids is important as per current established toxicity management guidelines.

If new or worsening pulmonary symptoms (e.g. dyspnea) or radiological abnormality suggestive of pneumonitis/interstitial lung disease is observed, the Dosing Modification and Toxicity Management Guidelines will be applied (appendix 4). The results of the full diagnostic workup (including high-resolution computed tomography (HRCT), blood and sputum culture, hematological parameters etc) will be captured in the eCRF. It is strongly recommended to perform a full diagnostic workup, to exclude alternative causes such as lymphangitic carcinomatosis, infection, allergy, cardiogenic edema, or pulmonary hemorrhage. In the presence of confirmatory HRCT scans where other causes of respiratory symptoms have been excluded, a diagnosis of pneumonitis (ILD) should be considered and the Dosing Modification and Toxicity Management Guidelines should be followed.

Pneumonitis (ILD) investigation

The following assessments, and additional assessments if required, will be performed to enhance the investigation and diagnosis of potential cases of pneumonitis. The results of the assessment will be collected.

- Physical examination: Signs and symptoms (cough, shortness of breath and pyrexia, etc.) including auscultation for lung field will be assessed.
- SpO₂: Saturation of peripheral oxygen (SpO₂)

When pneumonitis (ILD) is suspected during study treatment, the following markers should be measured where possible: ILD Markers (KL-6, SP-D) and β -D-glucan; Tumour markers: Particular tumour markers which are related to disease progression; Additional Clinical chemistry: CRP, LDHFor recurrente moderate (Grade 2) pneumonitis: permanently discontinue Durvalumab.

6.7.2.2. COLITIS

Colitis has been reported in subjects receiving Durvalumab.

Patients should be monitored for signs and symptoms of colitis or diarrhoea. Investigators are instructed to begin diarrhoea management early to minimise the risk of colitis.

6.7.2.3. HEPATITIS

Hepatitis has been reported in subjects receiving Durvalumab.

Immune-mediated hepatitis/hepatic toxicity is the inflammation of the liver. Hepatic AEs induced by PD-1/PD-L1 inhibitors commonly present as asymptomatic increase of AST and ALT, rarely total bilirubin. A proportion of patients may be presenting with fatigue, fever and radiologic appearances including hepatomegaly, periportal lymphadenopathy and periportal oedema.

6.7.2.4. NEPHRITIS

Nephritis has been reported in subjects receiving Durvalumab.

The major clinical syndromes produced by immune-mediated renal injury include nephrotic syndrome, rapidly progressive glomerulonephritis, and acute renal failure.

Signs and symptoms include increase in serum creatinine, decrease in urine output, peripheral oedema, haematuria, loss of appetite

6.7.2.5. ENDOCRINOPATHIES

The clinical presentation of immune-mediated endocrinopathies include hypothyroidism, hyperthyroidism, type 1 diabetes mellitus and nonspecific symptoms of headache and fatigue, but may also include myalgias, visual field defects, behavioural changes, electrolyte disturbances, loss of appetite and hypotension. Patients will generally have abnormal endocrine laboratory test results that include thyroid-stimulating hormone, free T4, total and free T3, cortisol, adrenocorticotropic hormone, luteinising hormone, folliclestimulating hormone, and testosterone.

6.7.2.6. SEVERE SKIN REACTIONS (RASH, DERMATITIS)

Immune-mediated severe skin reactions has been reported in patients treated with Durvalumab.

Immune-mediated dermatitis is generally mild and presents as mild local or diffuse maculopapular, erythematous rash on the trunk or extremities, which may be accompanied by pruritus, alopecia, and vitiligo, suggestive of inflammatory response to melanocytes.

For rash and dermatitis: prompt treatment with steroids (topical or systemic based on severity) is important.

In rare cases, severe dermatitis has been reported to manifest as Stevens-Johnson syndrome, toxic epidermal necrolysis, or rashes complicated by dermal ulceration or necrotic, bullous, or haemorrhagic manifestations. In such cases, withhold Durvalumab and refer the patient for specialized care for assessment and treatment.

If diagnosis is confirmed, permanently discontinue Durvalumab.

6.7.2.7. IMMUNE-MEDIATED MYOCARDITIS

Investigators should exercise clinical judgment in managing actual patients alongside the guidelines presented in the protocol(s). An event that exhibits rapid progression and/or the likelihood for high morbidity/mortality requires that clinical judgment be exercised above and beyond toxicity management guidelines to ensure that treatment is optimally tailored to any given patient's specific case.

For example, the general principles outlined in the toxicity management guidelines describe prompt initiation of corticosteroids for both Grade 2 events (that have persisted for 4-5 days) and Grade 3-4 events; clinical judgment applied to this baseline guidance for an event that exhibits rapid progression and/or the likelihood for high morbidity/mortality – such as myocarditis – would warrant prompt initiation of high-dose corticosteroids without delay even for grade 2 cases. Similarly, clinical judgment for patients with suspected myocarditis should lead investigators to obtain a cardiology consult and institute a thorough diagnostic work-up (that includes exclusion of other alternate causes such as infection), and the appropriate management that includes discontinuing drug (permanently if biopsy-proven immune-mediated myocarditis) and, as already noted, the prompt use of steroids or other immunosuppressives.

6.8. Packaging and Labeling

The following information will appear on the labels:

- Name of the Sponsor.
- Study number/Patient number.
- Dosage and route of administration.
- Quantity or contents of container.
- Batch number/packaging number.
- Expiration date and storage conditions.
- Local legal information, as appropriate.

6.9. Supplies and Drug Accountability

Trabectedin and Durvalumab will be supplied to investigators.

For ordering study drugs, please confer process of this study and pharmaceutical procedure.

Proper drug accountability will be done by the clinical trial monitor. Each study site will keep records to allow a comparison of quantities of drug received and used at each site. The Investigator at each study site will be the person ultimately responsible for drug accountability at the site.

All unused drug supplied by the Sponsor will be properly destroyed at the study site, at the end of the study. The documentation of this procedure must be provided to the clinical trial monitor.

6.10. Treatment Compliance

The Investigator is responsible for supervising compliance with the instructions described in this study protocol.

CONFIDENTIAL

7. STUDY EVALUATIONS

Study evaluations aim to assess:

- Diagnosis
- Efficacy
- Safety

7.1. Central review for diagnosis of soft-tissue sarcoma

7.1.1. Diagnosis of soft-tissue sarcoma

If diagnosis of sarcoma was not confirmed by the RRePS Network, pathological central review will be performed to confirm histological diagnosis of soft-tissue sarcoma by [name] and collaborators, Department of Pathology, Institut Bergonié, Bordeaux, France. The reviewer will assess the pathological diagnosis, document the results on the 'Pathological request form' response completed and sign this form.

Every discrepancy will be discussed between referral investigator, [name] or collaborators and the Sponsor, until a final decision is reached. Patients with diagnosis different from soft-tissue sarcoma will be considered ineligible and will not be included in the study.

7.1.2. Pathological specimen sampling necessary for central review

For a gross description and diagnostic information concerning pathological specimens, reference to "Recommendations for reporting soft-tissue sarcomas" is strongly advised (Recommendations, 1999). Available tumor samples obtained at diagnosis or at relapse, as unstained slides (10), and/or preferable paraffin-embedded tumor blocks (one or two) are mandatory for central review.

7.1.3. Pathological process schedule and implementation (not applicable if diagnosis reviewed in the RRePS Network)

Each site will send to Institut Bergonié within 7 days after the signature of informed consent:

- A completed pathology request form
- 10 unstained slides and/or preferable FFPE (Formalin-Fixed Paraffin-Embedded) block of specimen tumor sampling, obtained anytime during disease development
- Initial pathology report with patient code and date of birth (including macroscopic description) and pathology report of molecular biology if any.

All material must be sent to:

Institut Bergonie - Service Pathologie

Technicienne Anapath Recherche Clinique

Protocole TRAMUNE

[name]

Tél: [contact]

7.2. Efficacy – Expansion cohort only

The antitumor activity of trabectedin given in combination with durvalumab will be evaluated as per RECIST v1.1, in terms of objective response under treatment, best overall response, 6-month objective response, 6-month progression-free status, , 1-year PFS and OS.

7.2.1. Assessing Objective Tumor Response (RECIST v1.1)

- A comprehensive workup will be performed at baseline and every six weeks.
- Whenever the response criteria are met, the appropriate imaging tests will be repeated at least four weeks later in order to confirm the response.
- The same method will be used to evaluate each identified lesion both at baseline and throughout the study.
- Treatment will be administered as long as no disease progression or unacceptable toxicity is found, or as long as no other reasons for treatment discontinuation are met.
- Assessment of efficacy will be essentially based on a set of measurable lesions identified at baseline as target lesions and followed until disease progression and following the RECIST v1.1 criteria (Eisenhauer, 2009).

7.2.2. Centralized Radiological Review (Institut Bergonié)

7.2.2.1. GENERAL PROCEDURE

Centralized radiological review will be performed to confirm disease status in comparison with baseline, Week#6, Week#12, Week#18, etc.... For patients included in the reference center, CT scan will be initially read by a radiologist who differs from the expert.

Review process will be centralized at Institut Bergonié and will be performed by a radiologist expert in soft tissue sarcomas. The judgment provided by the expert reviewer will be retained and used in statistical analyses.

7.2.2.2. REVIEW PROCESS SCHEDULE

All tumor evaluations will be sent as soon as they become available. Patient's information must be recorded on a provided imaging CD.

7.2.2.3. PRACTICAL IMPLEMENTATION

For each shipment, each media should be accompanied by the Radiological Forms provided by the Sponsor.

All CDs must be sent to the sponsor CRA as described in guidelines provided as a separate document.

7.3. Safety

Patients will be evaluable for safety if they have received at least one treatment administration. Safety will be evaluated using clinical examinations, which will comprise vital signs analysis, clinical assessment of AEs, changes in laboratory parameters (hematological and biochemical, including liver function tests) and any other analyses that may be considered necessary. Safety profile will be continuously followed during treatment up to 30 days after the last treatment administration or until the start of a new antitumor therapy, whichever occurs first. All AEs will be classified according to the NCI-CTCAE, v4.03.

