4.8. EVALUATION AT the END OF TREATMENT

The end-of-treatment visit will be scheduled 30 days (4 weeks) after the last treatment administration (a window of ± 1 week is allowed).

Regardless of the reason for discontinuation, the complete workup has to be done at the end-of-treatment visit. This will include the following assessments:

- Assessment of signs and symptoms.
- Complete physical examination.
- ECOG performance status.
- Vital signs [heart rate, blood pressure, weight and temperature].
- Hematology.
- Biochemistry.
- Urinalysis
- Calculated CrCl.
- Thyroid function

- CA 125 measurement
- Clinical and radiological tumor assessment (CT-scan/MRI) (except for patients with confirmed PD at discontinuation or who had started a new treatment).
- Intercurrent events and concomitant disease and treatments.
- Safety assessment (AEs).

Adverse events must be reported for 30 days after the last treatment administration or until the start of a new antitumor therapy, whichever occurs first. All SAEs occurring within 90 days of the last treatment administration or until the start of a new antitumor therapy, whichever occurs first, will be reported. Beyond this period of time, only those SAEs suspected to be treatment-related will be reported (see Section 11).

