6.6.3. Restrictions during study

6.6.3.1. CONTRACEPTION

The following restrictions apply while the patient is receiving study treatment and for the specified times before and after:

- **Female patient of child-bearing potential:**

Females of childbearing potential who are sexually active with a non-sterilized male partner must use at least 1 **highly** effective method of contraception (table below) from the time of screening and must agree to continue using such precautions for 180 days after the last dose of study treatment. Non-sterilised male partners of a female patient must use male condom plus spermicide throughout this period. Cessation of birth control after this point should be discussed with a responsible physician. Not engaging in sexual activity for the total duration of the drug treatment and the drug washout period is an acceptable practice; however, periodic abstinence, the rhythm method, and the withdrawal method are not acceptable methods of birth control. Female patients should also refrain from breastfeeding throughout this period.

- **Male patients with a female partner of childbearing potential:**

- Non-sterilized males who are sexually active with a female partner of childbearing potential must use a male condom plus spermicide from screening through 180 days after receipt of the final dose of study treatment. Not engaging in sexual activity is an acceptable practice; however, occasional abstinence, the rhythm method, and the withdrawal method are not acceptable methods of contraception. Male patients should refrain from sperm donation throughout this period.
- Female partners (of childbearing potential) of male patients must also use a highly effective method of contraception throughout this period (Table below).

N.B Females of childbearing potential are defined as those who are not surgically sterile (ie, bilateral tubal ligation, bilateral oophorectomy, or complete hysterectomy) or post-menopausal.

Women will be considered post-menopausal if they have been amenorrheic for 12 months without an alternative medical cause. The following age-specific requirements apply:

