6.7.2. Events of clinical interest and immune mediated adverse event (imeics)

Events of clinical interest of a potential immunologic etiology (imECIs) may be defined as an adverse event of unknown etiology, associated with drug exposure and is consistent with an immune phenomenon. imAEs may be predicted based on the nature of the durvalumab compound, its mechanism of action, and reported experience with immunotherapies that have a similar mechanism of action. Special attention should be paid to AEs that may be suggestive of potential imAEs. An imAE can occur shortly after the first dose or several months after the last dose of treatment.

If an imAE is suspected, efforts should be made to rule out neoplastic, infectious, metabolic, toxin or other etiologic causes prior to labeling an adverse event as an imAE.

All imAE should be reported to sponsor (see section 11.7).

imAE will be managed according to the toxicity management guidelines (appendix 4). Durvalumab will be delayed until if the adverse reaction remains at Grade 1 or less.

If another episode of a severe adverse reaction occurs, only Durvalumab will be permanently discontinued.

Patient requiring 2 delays of Durvalumab injection should go off protocol therapy.

Ir-AE are described in this section, but not limited to the items outlined below. For management, refer to the appendix 4 and to most updated Investigator Brochure.

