10.3. Serious adverse event and new information notification (responsibility of the investigator)

Serious adverse events, regardless of relationship to the study drugs, will be reported by the investigator in the patient's CRF.

The investigator will notify to the Vigilance Unit without delay about any serious adverse events or new events occurring:

- From the date of the informed consent is signed,
- During the whole patient treatment period as defined by the research,
- Until 90 days after the last dose of the IMP/studied treatments or until the start of a new antitumor therapy, whichever occurs first,
- Beyond this period of time, only those SAEs suspected to be related to the IMP or the research (other treatments used, diagnostic procedures, examinations carried out during the research) will be collected without any limitation in terms of deadline. Nonetheless, the Sponsor will evaluate any safety information related to the clinical trial that is spontaneously reported by an Investigator beyond the time frame specified in the protocol.
- Whenever possible the investigator will record the main diagnosis instead of the signs and symptoms.

Type of Event	Reporting procedure	Deadline for reporting to the sponsor
SAE	SAE Notification form + written report form if necessary	To be reported immediately to the sponsor
New information	Written report form	To be reported immediately to the sponsor
Pregnancy	Pregnancy Notification form + Written report form if necessary	As soon as pregnancy is confirmed

The investigator must complete the "Serious Adverse Event Notification Form" (Appendix 5) immediately, in English, and assess the relationship with the study treatment. The form must then be dated, signed and sent by fax to the following address without delay to:

CELLULE DE VIGILANCE (VIGILANCE UNIT) – R&D UNICANCER

[contact]

Or contact : R&D Unicancer – Mail : [name]

For each event, the investigator will record:

- A description of the event that is as clearly as possible, using medical terminology,
- Date AE met criteria for serious AE, the date the event ended
- Date of the serious adverse event notification form report - The steps taken and whether or not corrective treatment was required, whether or not the investigational treatment was discontinued, etc.
- Date of hospitalization
- Date of discharge
- Probable cause of death
- Date of death
- Autopsy performed
- The patient's relevant medical history
- Concomitant medications / therapies

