10.4. Reporting pregnancy cases occurred within the clinical trial

Pregnancy and suspected pregnancy (including a positive pregnancy test regardless of age or disease state) of a female patient or the female partner of a male patient occurring while the patient is on study drug, or within 90 days from the patient's discontinuation visit, are considered immediately reportable events.

The Investigator will report the following events immediately and always within 24 hours from first knowledge:

- Any occurrence of a pregnancy where any kind of exposure to the IMP is suspected,
- Possible exposure of a pregnant woman (this could involve a partner of a male patient or a pregnant female who came in contact with the clinical trial IMP),
- All reports of elevated/questionable or indeterminate beta human chorionic gonadotropins (β -hCGs).

Immediately after detecting a case of suspected pregnancy in a female clinical trial patient, the decision on her continued participation in the clinical trial will be jointly taken by the trial patient, the Investigator and the Sponsor, with the patient's best interest in mind. A decision to continue the pregnancy will require immediate withdrawal from the trial.

Any pregnancy, suspected pregnancy, or positive pregnancy test must be reported to the Vigilance Unit immediately by facsimile using the Pregnancy Report form (appendix 7). In the case of pregnancy of the female partner of a trial patient, the Investigator will obtain her consent to provide the information in these situations.

The Investigator will follow the pregnancy until its outcome, and must notify the Vigilance Unit the outcome of the pregnancy within 24 hours of first knowledge as a follow-up to the initial report.

For any event during the pregnancy which meets a seriousness criterion (including fetal or neonatal death or congenital anomaly) the Investigator will also follow the procedures for reporting SAEs (complete and send the SAE form to the Vigilance Unit by facsimile within 24 hours of the Investigator's knowledge of the event).

All neonatal deaths that occur within 90 days of birth should be reported, without regard to causality, as SAEs. In addition, any infant death at any time thereafter that the Investigator suspects is related to the exposure to the study drug/IMP should also be reported to the Vigilance Unit by facsimile within 24 hours of the Investigators' knowledge of the event.

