10.7. Reporting events of clinical interest and immune-mediated adverse events

Information on how to identify and evaluate imAE/imAEs has been developed and is included in appendix 4. All imAE imAEs should be reported to sponsor.

ImAE observed with durvalumab include:

- Colitis, Intestinal perforation
- Pneumonitis
- ALT/AST increases / hepatitis / hepatotoxicity

Increase of AST and ALT should be reported as event of clinical interest if it meets the criteria of seriousness such as hospitalization and especially if treatment was given because of the event.

- Neuropathy / neuromuscular toxicity (i.e. events of encephalitis, peripheral motor and sensory neuropathies, Guillain-Barré, and myasthenia gravis)

- Endocrinopathy (i.e. events of hypophysitis, adrenal insufficiency, and hyper- and hypothyroidism, type I diabetes mellitus)
- Dermatitis
- Nephritis
- Pancreatitis (or labs suggestive of pancreatitis - increased serum lipase , increased serum amylase)
- Rash / dermatitis (including Stevens-Johnson syndrome, toxic epidermal necrolysis, rashes complicated by dermal ulceration or necrotic, bullous or haemorrhagic manifestations)
- Myositis/Polymyositis
- Vasculitis
- Non-infectious meningitis
- Non-infectious encephalitis
- Other inflammatory responses that are rare with a potential immune-mediated aetiology include, but are not limited to, myocarditis, pericarditis, uveitis, haematological events, sarcoidosis and rheumatological events.

In addition, infusion-related reactions and hypersensitivity/anaphylactic reactions with a different underlying pharmacological etiology are also considered AESIs.

The investigator will notify the Vigilance Unit without delay about any events of clinical interest.

The investigator must complete the specific form (Appendix 6) immediately, in English. The form must then be dated, signed and sent by fax to the following address without delay to:

CELLULE DE VIGILANCE (VIGILANCE UNIT) – R&D UNICANCER

[contact]

Or contact : R&D Unicancer – Mail : [name]

Adverse events that are both an SAE and an imAEimAEs should be reported one time as an SAE only, however the event should be appropriately identified as an imAEimAEs too in the database.

10.8. report of Non serious adverse event

TYPE OF EVENT	REPORTING PROCEDURES	DEADLINE FOR REPORTING TO THE SPONSOR
Non-serious AE	Case report/record form	Does not need to be reported immediately

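### Late non-serious imAEs have no dated CRF collection rule: general AE reporting ends at day 30, imAEs are reportable with no end date, and the SAP has no imAE table

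*Protocol*

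**What the plan says.** **General AE rule.** Protocol 4.8: "Adverse events must be reported for 30 days after the last treatment administration or until the start of a new antitumor therapy, whichever occurs first". Section 7.3 describes safety follow-up with the same end point: "Safety profile will be continuously followed during treatment up to 30 days after the last treatment administration".

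**SAE rule.** Protocol 10.3 sets the SAE window: "Until 90 days after the last dose of the IMP/studied treatments or until the start of a new antitumor therapy, whichever occurs first". After that, SAEs suspected to be related are still collected, with no time limit (4.8, 10.3).

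**imAE rule.** Protocol 6.7.2: "An imAE can occur shortly after the first dose or several months after the last dose of treatment". The same section wants every imAE reported to the sponsor, and 10.7 repeats this: "All imAE imAEs should be reported to sponsor". Neither gives an end date. Section 10.7 sends events of clinical interest to the Vigilance Unit on the Appendix 6 form. For AST/ALT increases it narrows the duty to those that meet a seriousness criterion.

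**Analysis.** SAP 3.2.3 builds the toxicity outputs from the CRF adverse event form. SAP 4.3.11 and 4.3.12 list AE and SAE tables and none for imAEs.

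**Pregnancy.** Under 10.4, a pregnancy is immediately reportable when "occurring while the patient is on study drug, or within 90 days from the patient's discontinuation visit". Under 6.6.3.1, female patients of childbearing potential "must agree to continue using such precautions for 180 days after the last dose of study treatment", and male patients have the same 180 days.

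**The concern.** The protocol says that one class of events can begin months after dosing, yet its general AE rule closes at day 30. A site with a non-serious thyroid or skin imAE starting on day 45 finds no duty to record it in 4.8 or 7.3, and a duty to report it in 6.7.2 and 10.7. Sites may resolve this differently, so late imAE counts could depend on local reading.

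The safety profile is part of the primary objective (Protocol 2.1), and the RP2D is to draw on safety data from all escalation and expansion patients (3.2, 3.4). Immune toxicity is the component that durvalumab can be expected to add to trabectedin. With 15 patients planned per expansion cohort, one patient is 1/15 = 6.7 percentage points, so a single unrecorded event would show in the reported percentages.

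The pregnancy question is of the same kind but smaller: a dated clause closes before the contraception period does.

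**Working it through.** The plan states no figure to reproduce. The check is day arithmetic from the last dose, with the rules set side by side.

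**1. Which late events have a rule**

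| Event starting after day 30 | Rule | End date |
|---|---|---|
| SAE, any cause | 4.8, 10.3 | Day 90, or new antitumor therapy if earlier |
| SAE, suspected related | 4.8, 10.3 | None |
| Non-serious AE, not an imAE | 4.8, 7.3 | Already closed |
| Non-serious imAE | 4.8 and 7.3: closed. 6.7.2 and 10.7: reportable | None stated |

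Only the last row contains a conflict. Day 30 to day 90 gives 90 − 30 = 60 days in which SAEs have a dated rule and non-serious imAEs do not. Both dated windows also close at new antitumor therapy, so the conflict can begin before day 30.

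**2. How far the 30-day rule falls short of the stated risk period**

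The protocol puts no number on several months. Assuming 60 to 180 days:
- shortfall of a 30-day rule: 60 − 30 = 30 days, up to 180 − 30 = 150 days;
- shortfall of a 90-day rule: none at 60 or 90 days, up to 180 − 90 = 90 days.

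A 90-day window therefore narrows the gap but may not close it.

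**3. Whether a notified imAE reaches the analysis**

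- The Appendix 6 form goes by fax to the Vigilance Unit (10.7). The SAP toxicity outputs come from the CRF adverse event form (SAP 3.2.3).
- Section 10.7 asks for an imAE marker in the database for events that are also SAEs. It says nothing equivalent for non-serious imAEs.
- The variables listed in SAP 3.2.3 include no imAE marker, and SAP 4.3.11 and 4.3.12 include no imAE table.
- Section 10.8 puts non-serious AEs on the CRF but gives no window of its own.
- The schedule of assessments ends with the end-of-treatment visit. Later follow-up is every 12 weeks without progression and every 6 months after progression or new therapy (4.4, 4.9). No contact is fixed at day 90.

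**4. Pregnancy clause**

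The discontinuation visit is taken as the end-of-treatment visit, day 30 ± 7 (4.8). Clause end = visit day + 90; gap = 180 − clause end.
- Visit on day 23: ends day 113, gap 67 days.
- Visit on day 30: ends day 120, gap 60 days.
- Visit on day 37: ends day 127, gap 53 days.

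Two other readings widen the gap. If the discontinuation visit meant the last-dose visit, the gap is 180 − 90 = 90 days. Inclusion criterion 13 counts six months from treatment discontinuation, which 4.4 defines as last dose + 30 days. That gives 30 + 182.6 = day 212.6, and 212.6 − 120 = about 93 days.

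**The case against.** The strongest reply is that the protocol already covers these events.

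- **imAEs have a route.** Sections 6.7.2 and 10.7 set a specific duty with no end date, and Appendix 6 accepts grades 1 to 5 with no seriousness condition. Section 4.8 sets a minimum and does not forbid later reports, so a site that notifies a day-50 event breaks no rule. This stands. A reader might infer that non-serious imAEs are not collected at all after day 30; the documents do not support that.
- **The SAP has no AE cut-off date.** The safety population is every treated patient (SAP 2.4), the listing in SAP 4.1.2 runs beyond cycle 1, and the AE tables carry no date limit. This also stands. A late imAE entered on the CRF would be analysed. The weakness is that no dated rule ensures its entry and no output separates it from other AEs.
- **Dose decisions may be unaffected.** DLTs and the MTD rest on the first 21 days, and the RP2D is a trabectedin level with durvalumab fixed. A reader might infer that the RP2D will be distorted, or that late imAEs are under-counted mainly in patients who stop early. The documents give no late imAE frequency, so neither can be shown.
- **Pregnancy reporting does not stop.** Section 10.2.8 requires exposure during pregnancy to be reported in every case, including pregnancy found after the product was stopped. Section 10.4 also makes any pregnancy with suspected IMP exposure reportable within 24 hours with no end date, and the 10.3 table sets no cut-off. A reader might infer that pregnancies after about day 120 go unreported; these clauses contradict that. What remains is that nothing says whether, for example, conception on day 150 counts as exposure, while 10.4 also contains a dated clause that has closed by then.

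**Conclusion.** The point holds for non-serious imAEs that start after day 30, or after an earlier new antitumor therapy. Sections 4.8 and 7.3 close general AE reporting, while 6.7.2 and 10.7 leave imAE reporting open. A late event can be notified to the Vigilance Unit and still be absent from the CRF data on which the safety profile rests, with every instruction followed. The SAE rules do not fill this gap, because they apply only to serious events.

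The measurable size is the 60 days between the AE and SAE windows. The shortfall against several months is 30 to 150 days if that phrase means 60 to 180 days, which is an assumption. The number of events affected cannot be estimated from the documents. Sample size and the 21-day DLT assessment are untouched; the effect is on the completeness of late immune toxicity data. It should be corrected.

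The pregnancy clause is secondary: an inconsistency of 53 to 67 days on the main reading, to be resolved by aligning the text.

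**What to change.** 1. In Protocol 4.8, 7.3 and 10.7, except imAEs from the 30-day limit. Collect imAEs of any seriousness actively on the CRF to at least 90 days after the last dose, which is the existing SAE window. Do not end imAE collection at new therapy; flag events that start after it.
2. Keep the undated duty to report imAEs that start later, since 90 days may still be shorter than the stated risk period.
3. Add an imAE marker to the CRF adverse event form for non-serious events too. Add a table of imAEs by type, grade and time from last dose to SAP 4.3.11, with those after new therapy shown separately.
4. Reconcile the dated pregnancy clause in 10.4 with 6.6.3.1, inclusion criterion 13 and 10.2.8, so that one reporting period is stated and it is clear when a pregnancy after treatment counts as exposure.

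**Cost:** amendment wording, a few more CRF entries, one SAP table, and a contact at about day 90. That contact is not on the visit schedule, although the 90-day SAE rule already implies it.
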